#### **4.6 Implementation of the Cancer Prevention CDS Intervention**

Throughout the implementation of the CP-CDS, we will conduct key informant and patient interviews, surveys, usability testing, and continuous quantitative and qualitative feedback between researchers and participants to measure the implementation processes and outcomes as recommended by the CFIR and RE-AIM frameworks. **Organizational Engagement:** In Phase 1, we will engage EH clinic leadership and managers, informatics personnel, PCPs, CMAs, and patients through meetings to identify potential influences of implementation of this project. **Pilot Testing:** All CP- CDS algorithms and interfaces will be extensively pilot-tested among stakeholders in Phase 2 to adapt the implementation. Representatives from EH Patient Councils will evaluate the patient interfaces to maximize patient-centeredness. We will then recruit two EH clinics not in the study and pilot test CP-CDS in eligible patients for 4 weeks. We will conduct in-depth interviews with up to 10 PCPs at the two pilot clinics pre- and post-pilot, asking probing questions about shared decision-making and shared decision-making tools. After further modification of the CP-CDS, the project will enter Phase 3. **EH Patient Advisory Councils:** EH has 18 volunteer patient advisory councils that engage patients and families as advisors, mentors, and educators. The main goal of this program is to improve the patient and family experience and quality of healthcare. Research team members will recruit representative members to regularly review and critique project pilot phase activities, CDS interfaces, survey tools, interview objectives and results, and project deliverables. This existing infrastructure is ideal for introducing CDS technology to primary care, gaining the reaction and input of patients and families, and refining adaptation of the intervention.

**Implementation of the Cluster-Randomized Trial (Phase 3):** We will train intervention clinics to use CP-CDS using strategies similar to those EH routinely uses to inform clinic teams of changes to the EHR. They include face-to-face group or individual meetings with all intervention clinic PCPs, CMAs, and clinic staff, plus email reminders with links to a short instructional video demonstrating CMA and PCP roles in CP-CDS use. Training will be completed and CP-CDS fully implemented at the 24 intervention clinics within 30 working days of the project "go-live" date.

**Strategies to Ensure PCP Care Team Use of the Intervention:** Following implementation, all intervention clinic staff will receive monthly email reports showing CP-CDS use rates. Study team personnel will have ongoing communication with the intervention clinic nurse managers throughout the duration of the intervention period to assess continued use of CP-CDS and to gather feedback ensuring real-time observation of implementation fidelity. Support from EH leaders and clinic PCP leaders, plus monitoring and feedback, will help maximize provider adherence to CP-CDS study protocols, as demonstrated by CDS use at 75%-80% of targeted visits in previous projects.

To further encourage use of the tool, clinics will be offered a best practice lunch and learn for printing at goal. If a clinic achieves four non-consecutive months at or above 75% print rate, the Wizard team will provide a catered project-related meeting. The Wizard team will provide a meeting agenda for the clinic manager and/or nurse supervisor with the expectation that notes from the meeting will be returned to the Wizard team. This lunch and learn will also be offered at 10 non-consecutive months at or above 75% including the previous four.

Additional quality assurance (QA) will be conducted to ensure appropriate functioning of the Wizard algorithms, which determine clinical recommendations made by the Wizard to the provider and patient. The QA will require manual review of select patients' electronic medical records. Key study personnel at Essentia Health will be responsible for the review. Manual chart review may also be required during implementation if necessary for QA of Wizard algorithms. Information reviewed during QA will not be retained for study analyses.

**Evaluation of Implementation Process and Outcomes (Phase 4):** During the cluster-randomized trial, components of the RE-AIM and CFIR frameworks will be assessed to determine mediators of CP-CDS implementation, use, clinical outcomes, and future strategies for dissemination and implementation.

#### **4.7 Definition and Measurement of Dependent Variables**

We will use a mixed-methods approach to determine the facilitators and barriers for achieving the specific aims. Appendix A contains the definitions, sources, and metrics for study variables.

**Cancer Screening Tests (Aim 1, H1):** The dependent variable for H1 is a binary variable indicating that the patient is up to date on the specific constellation of screening tests for breast, cervical, lung and colorectal cancer that were due at the index visit for the patient by 12 months after the index visit. Secondary endpoints for H1 will look at the same individual screenings, within 12 months of the index visit. Each patient will be classified as up to date or not (composite endpoint) on all appropriate screening tests, depending on sex, age, risk factors, and date of last needed screening tests according to active USPSTF recommendation statements. This variable will be based on EHR-captured procedure codes that are routinely gathered by the Wizard interface at actual and re-run visits, which manually force the capture of this data into the Wizard repository, and data will be obtained from the index visit date through 12 months past the last patient index date.

**HPV Vaccination Rates (Aim 1, H2):** New CDC recommendations put into effect at Essentia Health January, 2017 are reflected in changes to the HPV vaccination sample and recommendations in this study. Children ages 9-14 are now recommended to receive 2 HPV vaccine doses, while 3 HPV vaccine doses are still recommended for adolescents and young adults ages 15-26. The dependent variable for H2 is a binary variable indicating that the patient has had all 2 or 3 HPV vaccinations recommended by ACIP/CDC, dependent on age group, within 12 months of the index visit. This variable will be coded as "1" for patients having all 2 or 3 vaccinations and "0" for patients with 0-2 vaccinations, dependent on age group. HPV vaccination data will be obtained from the EHR from the index visit date through 12 months past the last patient index date.

**12-month Health Care Costs (Aim 2, H3):** Costs for this analysis are defined as intervention costs as well as the incremental medical care costs associated with the intervention from the health system

perspective.

Intervention costs include CDS implementation and maintenance, training, and incentives but exclude intervention research and development costs. Medical care costs include costs of all medical services-including laboratory, physician services, and screening tests-incurred in the 12-month post-index date period by participants in each study group, as indicated by EH billing and clinical encounter data. Described in detail in the Section 4.9.3 below, we will use relative value units (RVUs) and diagnosis-related groups (DRG) to calculate inpatient and outpatient costs for patients randomly assigned to each study group and standard accounting methods to measure the cost of the CP-CDS intervention. Emergency visits and hospitalizations may be too infrequent in the study sample to accurately predict a population-wide impact of the study interventions. If there were no intervention impact on these utilization components during the study period, including their costs would substantially increase variance in the cost data without adding to the accuracy of the cost assessment. Therefore, we will first assess whether there is a differential impact between CP-CDS and usual care on use of these services and will include their costs only if a difference is observed. Reliance on EH billing records for measuring medical care use may miss costs incurred in other health systems; however, this opportunity is expected to be equal across randomized study arms, and cross-system medical utilization is expected to be relatively limited in the primarily rural study population.

While market prices generally are a good estimate of the costs for medical services, the paid amount in this claims system is specific to HealthPartners at a particular time and may provide a biased view of costs between pre- and post-intervention periods. To address this, we will use Total Care Relative Resource Values™ (TCRRVs), which are a nationally standardized set of measures that have been endorsed by the National Quality Forum and are derived from Centers for Medicare and Medicaid Services (CMS) relative value units (RVUs). TCRRVs extend CMS RVU measures to include utilization categories, such as laboratory services and medications, which do not have CMS RVU weights. Specifically, TCCRVs defined during the midpoint of patient accrual and follow-up (e.g., 2019) will be used to convert claims to represent U.S. dollars.

**Health System Revenue (Aim 2, H4):** Use of ICD-10 diagnostic codes and CPT-4 billing codes during primary care visits in study clinics will be used to predict health system revenue collection. ICD-10 diagnostic codes include those for breast, colorectal, cervical and lung cancers; HPV vaccinations (3 codes: up to 3 vaccinations), obesity, and smoking. ICD-10 and/or CPT-4 codes for mammography, colonoscopy, stool-based tests for colorectal cancer, low dose CT lung scans, Pap test/cytology with and without HPV co-testing, referral to smoking cessation counselor, prescription of smoking cessation drugs (multiple), referral to weight management program, referral to dietitian, referral to bariatric surgery program. Coding complexity of clinical encounters will be measured by billing levels for evaluation and management services during clinic visits. Specifically, complexity levels will be measured using CPT-4 codes for new patients, from 99201 (level 1, low complexity) to 99205 (level 5, high complexity), and established patients, from 99211 (level 1, low complexity) to 99215 (level 5, high complexity).

**Facilitators and Barriers of Implementation (Aim 3):** For this analysis, we use the CFIR and RE-AIM frameworks to assess implementation process and outcomes. RE-AIM metrics are: a) percent and type of patients reached, b) for whom the intervention was effective, c) percent of clinics and providers that adopted the intervention, d) consistency and cost of intervention implementation, and e) proportion of intervention components and effects maintained. CFIR metrics include PCP perceptions of CDS source, strength and quality of the evidence base, iterative adaptability and testing of the CDS and usability testing; external policies and incentives affecting implementation; implementation climate and readiness; PCP engagement; fidelity of implementation and modifications made; and PCP knowledge, attitudes, beliefs, and self-efficacy about the CDS. Detailed descriptions of these metrics are in Appendix A.

Our mixed-methods approach includes: a) semi-structured interviews conducted with 8-20 EH leaders and 8-20 PCPs and CMAs during Year 1 to understand organizational support and culture to guide CDS implementation and Year 4 to plan future dissemination; b) meeting minutes from organizational engagement and study implementation, c) patient interviews during Years 2-4 (patients recruited from the CDS arms) to learn about their experiences with the CDS and perceived barriers and facilitators to act on the CDS personalized recommendations; d) interviews with PCPs and CMAs at intervention clinics as part of key stakeholders interviews in Year 2 and interviews with PCPs and CMAs at intervention clinics in Years 3-4 to learn how to improve CDS use, effectiveness, and dissemination to other clinics; e) pre- and post-pilot in-depth interviews with up to 10 PCPs in pilot clinics; f) cross-sectional PCP surveys conducted in Year 1 before randomization (pretest) and Year 4 (post-test) among PCPs in each study arm (approximately 400

total) to assess perceptions of primary practice systems related to cancer screening and prevention, including PCP demographics, experience, and use of CDS; g) in Year 4, PCPs in Arms A, B, & C will complete the 10 item System User Scale (SUS, Appendix C) to assess their experience with the CDS, as well as questions presented in the baseline surveys; and h) patient surveys in Years 2-4 on a cohort of up to 100 from each arm (approximately 300 total) to assess their experience with cancer prevention and screening care in their primary care clinics. In addition to questions on primary (tobacco cessation, weight management, and HPV vaccination) and secondary (breast, cervical, colorectal, and lung) cancer prevention and screening care at Essentia Health, the survey will contain demographic questions, questions adapted from the Clinic and Group Consumer Assessment of Healthcare Providers and Systems (CG-CAHPS, Appendix C) and from the 10-item Decisional Conflict Scale (O'Conner, 1993, revised 2005). Patient consent will be implied by survey completion. Patient survey eligibility criteria include being eligible for the survey during their CP-CDS index visit (or comparable visit at the study control clinics) and completing the survey. Those patients that complete the survey will be offered their choice of a mailed \$10 gift card to Target or an emailed e-gift card to Walmart. Patients will be mailed a letter on the study, a paper survey, and a \$2 incentive approximately 15 days from their index visit. Patients who do not respond to the mailed paper survey may be called up to 7 times by the Survey Research Center at HealthPartners Institute, where they will receive an option to take the survey over the phone. All surveys will be administered and tracked from the Survey Research Center. See the CPW Patient Survey Protocol\_2018-06-29\_FINAL.pdf document for complete details.

**Dependent Variables for Secondary Analyses:** In Appendix A, primary and secondary dependent variables are defined, some of which assess potential moderators of intervention effects. Secondary analyses include (a) rural-urban comparisons, (b) separate binary outcomes for the 3 screenings tested as a composite in H1: colorectal, breast, and cervical cancer, (c) lung cancer screening, (d) a binary outcome of any HPV vaccinations vs. none within 12 months of the index date, and (e) binary indicators for referrals to internal or community programs for , smoking cessation, or medications prescribed for smoking cessation, (f) smoking cessation by 12 months following the index date.

**4.8 Measurement of Independent Variables Primary Predictor:** The primary predictor is the treatment arm to which a clinic is randomized. This variable will be coded as a two degree of freedom contrast with the usual care (UC) arm as the reference category. Planned contrasts will examine pairwise differences in treatment arms. **Patient and Provider Characteristics:** Patient and provider characteristics listed in Appendix A will be documented so we can assess the extent to which results apply to subgroups of patients or whether patient or PCP characteristics modify intervention efficacy. Patient sex will be an important covariate and stratifying factor in the analysis because screening rates for H1 are likely to be different by sex. Clinic randomization may introduce random or selection-induced patient or PCP covariate imbalance, necessitating adjustment. Patient characteristics obtained from the EHR, include demographics, pre-intervention comorbidities (derived from dated ICD-10 diagnosis codes), insurance status, smoking status, among others. Furthermore, primary care visit dates will link patients and PCPs. We will have complete data for PCP characteristics, including age, sex, race, ethnicity, physician or allied provider (i.e., nurse practitioner), department.

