**Specific Aim 1.** Conduct a cluster-randomized trial that includes 36 primary care clinics (34 randomized clinic units, with 3 clinics randomized together due to shared providers) with approximately 300 PCPs and more than 153,000 patients to one of three study arms: (a) PCP-Focused Group: PCP intervention using an EHR-linked, Web-based CP-CDS system, (b) shared decision-making tools (SDMT) Focused Group: PCP intervention using an EHR-linked, Web-based CP-CDS system including additional, or (c) usual care (UC) to assess whether this intervention can improve the delivery of evidence-based, personalized primary and secondary cancer preventive care in rural primary care settings. Specifically, the PCP-focused group will receive a point of care CP-CDS tool that is integrated into the EHR. The CP-CDS provides evidenced-based recommendations to the provider and patient related to overdue cancer prevention screening services and eligible for smoking cessation and obesity management referrals. The SDMT-focused group will also receive the CP-CDS. Furthermore, the SDMT-focused arm provides SDMT to the patient and provider at the time of the visit. The UC arm will not receive the CP-CDS or SDMT but will receive usual best practice advisory suggestions for cancer prevention screening and other usual care.

**Hypothesis 1 (H1).** Eligible study subjects will have significantly different rates of appropriate screening tests for breast, colorectal, and cervical cancer as defined by the U.S. Preventive Services Task Force (USPSTF) during the 12 months after the index visit by study arm, with PCP-focused group higher than UC and SDMT-focused group higher than UC.

**Hypothesis 2 (H2).** Eligible study subjects will have significantly different rates of human papilloma virus (HPV) vaccination in appropriate cases, as defined by the Advisory Committee on Immunization Practices/Centers for Disease Control and Prevention during the 12 months after the index visit by study arm, with PCP-focused group higher than UC and SDMT-focused group higher than UC.

**Specific Aim 2.** Assess the cost of the CP-CDS intervention from the health system perspective through measurement of healthcare utilization and use of diagnostic codes and billing levels related to cancer prevention services.

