**2.3 Preliminary Assessment of the Study Population:** Data collected 01/01/12 to 12/31/14 demonstrate that there will be a sufficient number of Essentia Health (EH) patients to power this cluster-randomized trial (Table 1).

In addition, EH PCP primary cancer prevention activity at the study site, based on data collected 01/01/14 to 12/31/14 show:

Referrals for smoking cessation services= 4.4% (1159 referrals/26,574 active smokers);

Prescriptions for quit smoking drugs= 7.1% (1901 prescriptions/26,574 active smokers);

Referrals to dieticians or weight management programs = 1.9% (1521 referrals /80,730 patients with BMI >25.0 kg/m^2).

**Table 1. Clinical Status of Essentia Health Patients aged 11-80 with 2+ primary care visits within 36 months, by age group, smoking status, obesity rates, rural-urban residency, and cancer prevention procedure\*\***

Cancer screening/ prevention, ages	N patients eligible for screening*	% Up to date on screening or HPV vaccination 	% Current smoker	% Obese 	Rural N (%)	Urban N (%)
Colorectal, 50-75	87,019	67.1	16.5	45.6	52,368 (60.2)	34,651 (39.8)
Breast, 38-74	44,542	65.9	16.0	43.5	26,940 (60.4)	17,602 (39.6)
Cervix, 21-65	75,420	53.9	21.8	41.1	40,028 (53.1)	35,392 (46.9)
Subjects eligible for HPV vaccine, 11-26 	40,297	3 doses: 5.1 males, 19.5 females #	12.8	18.4	20,484 (50.8)	19,813 (49.2)

\*Patients with missing data are not included in denominator. Total patient population is significantly larger for all categories.

\*\*Data collection timeframe: Jan. 1, 2012 to Dec. 31, 2014

Patients who received cancer screening test or human papilloma virus vaccine

#1 or 2 doses of HPV vaccinations: 9.6% males, 30.1% females

BMI>30.0

NB: Lung cancer screening was not assessed in this preliminary data

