**4.12 Strengths and Limitations of the Study:** Valid EHR data are key to this project, and some data may be missing or inaccurate. However, dates of all mammograms, colonoscopies, and PAP/HPV tests and smoking history are updated by CMAs at each office visit and are easily retrieved to inform both the CDS and for use in the analyses. In previous studies, others and we have validated EHR-derived data elements needed in the analysis, and our study endpoints use easily validated data. Budgetary constraints limit the primary cancer prevention intervention strategy to HPV vaccination, with secondary analysis of smoking cessation. These potential limitations should be weighed against the strengths of this ambitious, timely, and innovative project. National and regional data show dramatic deficits in preventive cancer care, especially in rural areas; the counties in this study are ranked in the bottom half of the counties in Minnesota, North Dakota and Wisconsin in health status and outcomes. Unfortunately, EHR systems have failed to deliver consistent clinical benefits in outpatient settings. However, over a series of NIH-funded projects, we developed a scalable EHR-linked, Web-based CDS system that significantly improved important chronic disease outcomes. We now adapt this CDS system to cancer preventive care and posit that directing provider and patient attention to cancer prevention at the point of care will improve delivery of cancer prevention services in rural primary care clinics. Our 3-arm design also compares the effectiveness of workflows with and without SDMTs to engage patients in cancer preventive services; previous studies suggest better outcomes when clinic staff initiate discussion of preventive care services before the PCP encounter. Economic analyses are an additional study strength. Other strengths include use of RE-AIM and CFIR conceptual frameworks, our expertise in CDS programming and evaluation, and the size of EH's rural population in three states.

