## Appendix A. List of Dependent and Independent Variables.

Figure A.1. Variables for Analysis including Description, Data Source, and Classification. ICD-9 diagnosis codes will be replaced with ICD-10 diagnosis codes in 2015. Blue shaded variables are CFIR related metrics

Variable	Description	Data Source	Variable Classification
Dependent Variables			
Up-To-Date Cancer Screening	A binary variable indicating the patient is up to date on screening tests for breast, cervix, and colorectal cancer by 12 months following the index visit.	EHR Procedure Results from Wizard re-run	Binary
Up-To-Date Colorectal Cancer Screening	A binary variable indicating the patient is up to date on colorectal cancer screening by 12 months following the index visit.	EHR Procedure Results from Wizard re-run	Binary
Up-To-Date Breast Cancer Screening	A binary variable indicating the patient is up to date on breast cancer screening by 12 months following the index visit.	EHR Procedure Results from Wizard re-run	Binary
Up-To-Date Cervical Cancer Screening	A binary variable indicating the patient is up to date on cervical cancer screening by 12 months following the index visit.	EHR Procedure Results from Wizard re-run	Binary
All HPV Vaccinations Complete, age 18-26	A binary variable indicating the patient has had all HPV vaccinations as recommended by ACIP/CDC within 12 months of the index visit.	EHR Procedure Results from Wizard re-run	Binary
Some HPV Vaccinations Complete, age 18-26	A binary variable indicating the patient has had at least 1 HPV vaccination as recommended by ACIP/CDC within 12 months of the index visit.	EHR Procedure Results from Wizard re-run	Binary
All HPV Vaccinations Complete, age 9-17	A binary variable indicating the patient has had all HPV vaccinations as recommended by ACIP/CDC within 12 months of the index visit.	EHR Procedure Results	Binary
Lung cancer screening	A binary variable indicating the patient is up to date on lung cancer screening by 12 month following the index visit.	EHR Procedure Results from Wizard re-run	Binary
Any quit attempts	A binary variable indicating that the patient made any smoking quit attempts in the 12 months following the index date	Wizard EHR	Binary
Smoking status at 12 months	A binary variable indicating that the patient has a non-smoker smoking status at 12 months following the index date	Wizard EHR	Binary

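### H1 is worded as screening done in the 12 months after index but defined as an up-to-date status with no service-date rule, so older tests first recorded after index could count as successes, possibly more often in the CDS arms

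*Combined protocol and SAP*

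**What the plan says.** **Event wording.** H1 in the Specific Aims compares rates of appropriate screening tests "during the 12 months after the index visit by study arm". Section 4.9.1 likewise speaks of appropriate screening within 12 months of an index visit.

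**Status wording.** Section 4.7 defines the H1 variable as "indicating that the patient is up to date on the specific constellation of screening tests" that were due at the index visit, judged by 12 months after it. Classification is made "depending on sex, age, risk factors, and date of last needed screening tests according to active USPSTF recommendation statements". Appendix A (Figure A.1) uses status wording for the composite and for each single screen, for example "A binary variable indicating the patient is up to date on colorectal cancer screening by 12 months following the index visit". Section 4.7 describes the single-screen secondary endpoints as assessed within 12 months of index, so the two places also differ on those.

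**Source and window.** On the source, Section 4.7 says: "This variable will be based on EHR-captured procedure codes that are routinely gathered by the Wizard interface at actual and re-run visits". It adds that "data will be obtained from the index visit date through 12 months past the last patient index date". Section 4.9.5 describes the 12-month re-run as a snapshot of the EHR.

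**How test dates reach the record.** Section 4.12 says that "dates of all mammograms, colonoscopies, and PAP/HPV tests and smoking history are updated by CMAs at each office visit", and that these dates serve both the CDS and the analyses.

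**What differs by arm.** Section 3.5.1 gives usual-care clinics no access to the CP-CDS. In the CDS arms (Section 3.5.2, Step 5) an alert goes to the medical assistant (CMA), who prints sheets for the provider and the patient.

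**The concern.** An event endpoint and a status endpoint agree only if the record at index is complete. Take a patient flagged as overdue who in fact had a still-valid test that was never recorded. If that history is entered after index, the status endpoint turns from not up to date to up to date although nobody was screened during follow-up.

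That would be noise if it were equally common in all arms. Here the person who maintains the dates is also the person the CP-CDS alerts, and the patient is handed a sheet saying that the test is due. That invites the reply that it was done elsewhere. Usual-care clinics do not get this prompt. Better record-keeping in the CDS arms could then be read as more screening, in the primary endpoint and in the direction of the hypothesis. The plan contains no tabulation or sensitivity analysis that would reveal it.

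**Working it through.** **1. Does any passage exclude a pre-index test?**
- Section 4.7 classifies by the date of the last needed test but sets no lower limit on that date.
- The extraction window in Section 4.7 opens at the index visit date and closes 12 months after the last patient's index date. Its end is common to the whole study, so it is not a patient-level limit on service dates.
- Procedure codes are named as the source, but the text does not say that only codes with post-index service dates count. Section 4.12 says that staff-updated dates are used in the analyses.
- Only the Specific Aims and Section 4.9.1 imply an event after index, and they do not define the variable.

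The documents therefore support two different primary endpoints.

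**2. The plan's own scale (Section 4.9.2).** Inputs: 3133 men and 11,088 women per arm, 10 clinics per arm, ICC 0.005 to 0.02.
- Patients per arm: 3133 + 11,088 = 14,221. Per clinic: 14,221 / 10 = 1422.1.
- Design effect = 1 + (m − 1) × ICC. At 0.005: 1 + 1421.1 × 0.005 = 8.11. At 0.02: 1 + 1421.1 × 0.02 = 29.42.
- Effective n: 14,221 / 8.11 ≈ 1754, and 14,221 / 29.42 ≈ 483. The plan states 484 to 1754.
- Detectable rate against 11% (two-sided 0.05, 80% power, R-square 0 to 0.1, with and without continuity correction): 14.1% to 14.4% at n = 1754, and 17.3% to 17.9% at n = 484. The plan states 14% to 18%.

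The plan's figures reproduce. The detectable difference is 3 to 7 points, and the anticipated effect of the PCP-focused arm is 18 − 11 = 7 points.

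**3. Illustrative size.** The documents give no figure for either input, so both are assumptions:
- u = share of index-overdue patients with an unrecorded, still-valid older test: 2%, 5%, 10%.
- d = excess probability, CDS minus usual care, that it is entered within 12 months: 20, 30, 50 points.

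Spurious difference ≈ u × d:

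| u | d = 20 | d = 30 | d = 50 |
|---|---|---|---|
| 2% | 0.4 | 0.6 | 1.0 |
| 5% | 1.0 | 1.5 | 2.5 |
| 10% | 2.0 | 3.0 | 5.0 |

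(percentage points). Multiplying by 1 − 0.11 = 0.89, to allow for patients who would succeed anyway, gives 0.36 to 4.45. At d = 0 every entry is zero.

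**4. What such a shift would do.** With no true effect, an 11% base rate and two-sided 0.05, the chance of a significant result over effective n of 484 to 1754 is:
- 1 point: 8% to 15%
- 1.5 points: 11% to 28%
- 3 points: 29% to 77%

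As a share of the anticipated 7 points, 1 point is 1 / 7 = 14% and 3 points is 3 / 7 = 43%. These are conditional statements about assumed shifts, not estimates for this trial.

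**The case against.** The case against has several parts, and much of it stands.

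- **A post-index reading is natural.** The event wording, the procedure codes and the start of extraction at index all lean that way, and no passage says that a staff-entered historical date creates a procedure code. But the variable definition does not state the rule, and Section 4.12 says that staff-updated dates are used in the analyses. The gap remains.
- **Correction may come first.** Appendix C places the alert after the CMA has completed rooming and entered data. If test dates are updated during rooming (an inference), much history is corrected before a patient is classed as overdue. This stands and shrinks u.
- **The arm difference is not shown.** Section 4.12 describes date updating at each office visit without limiting it to CDS clinics, and usual care keeps its own reminders. This stands: if updating is equal, the bias is near zero.
- **Recording is said to be nearly complete.** Section 4.9.5 says incomplete recording is rare, even for care outside the system. It gives no figure, but the documents offer none to the contrary.
- **The composite dilutes the effect.** Success requires every due test, so one back-entered test converts only patients with no other test outstanding, and it must still be valid at 12 months. This stands, and it makes the upper end of the range less likely.

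Two stronger readings are tempting. A reader might take the Table 1 footnote, "Patients with missing data are not included in denominator. Total patient population is significantly larger for all categories", as evidence that screening histories are often incomplete. It does not say which data are missing, and leaving patients out of a feasibility denominator is not the same as misclassifying tested patients as overdue. A reader might also extend the point to H2. The support is weak: Section 4.7 already ties the HPV doses to the 12 months after index, and Appendix A collects vaccination dates before and after index for ages 9 to 17.

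**Conclusion.** The definitional gap is real. H1 is an event in two places and a status in two others, and no passage requires the qualifying test to have been performed on or after index. The route to an arm difference is credible because only the CDS arms get the CP-CDS prompt and sheets.

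A reader might go on to infer that the CDS effect will be inflated. The documents do not support that: they show neither that older tests will be entered more often in the CDS arms nor how many exist. The 0.4 to 5 point range rests wholly on the assumed u and d, ignores dilution by the composite, and serves only to show that a small imbalance would matter beside a 3 to 7 point detectable difference. The change is worth making because it concerns the primary endpoint, because any bias of this kind would favour the intervention, and because the plan as written could not detect it.

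**What to change.** 1. Reconcile the Specific Aims, Section 4.7, Section 4.9.1 and Appendix A. Count an H1 success, and success on each single-screen outcome, only when each test due at index has a service date from the index date through index + 12 months. Tests done elsewhere within that window still count.
2. Report by arm the number of patients who became up to date only through a pre-index service date. This measures the problem directly.
3. Add two sensitivity analyses: the present status-based definition, and one that treats the patients in item 2 as not due at index. Require the conclusion to hold across all three.

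Item 3 is needed because the date rule has a bias of its own. Coding corrected-history patients as 0 keeps people who were not truly due in the denominator. A usual-care patient whose history is never corrected may be retested and count as 1, while a CDS patient whose history is corrected is not retested and counts as 0. That works against the CDS arms.

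The cost is a change of wording, a filter on service dates, slightly lower event rates and a little more analysis. The sample-size formula does not change.
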